In our recently completed RELIEF trial, in which we enrolled near-identical patients to that proposed in this trial, the pooled incidence of SSI was 14% (consistent with global data²) and red cell transfusions were used in 12% of patients. An incidence of SSI of up to 25% has been reported in other at-risk major gastrointestinal surgical cohorts.43, 44 Assuming an incidence of 12%, and using a type I error of 0.05, we require 1,484 per group in order to have 90% power to detect a 30% reduction in SSI to 8.4% (i.e. relative risk 0.7). Were the control group incidence 14%, this sample size provides 94% power to detect a 30% reduction to 9.8%. We plan to enrol 3,300 patients. This will also provide ≥90% power to detect a 30% reduction in blood transfusions.

Assuming 30% of patients are diabetic and an incidence of SSI in non-diabetic patients in the placebo arm of 10%, this sample size provides \approx 70% power to detect a difference in treatment relative risks of 0.55 in non-diabetic patients and 0.94 in diabetic patients on the multiplicative relative risks scale.45

12. Framework

This trial uses a superiority hypothesis testing framework between groups for the primary outcomes. Results will be reported in accordance with the CONSORT 2025 statement.

13. Statistical interim analyses and stopping guidance

Interim analyses will consider the defined study and safety endpoints after enrolment of 50% and 75% of patients, adjusted according to the O'Brien and Fleming method. Results will be made available to the DSMC, consisting of experts in the fields of surgery, infectious diseases and anaesthesia, and an independent statistician (Chair: [name], UK).

Section 4: Statistical Principles

14. Level of statistical significance

All applicable statistical tests will be 2-sided and will be performed using a 5% significance level.

15. Description of any planned adjustment for multiplicity, and if so, including how the type 1 error is to be controlled

No adjustment for multiplicity is planned.

16. Confidence intervals to be reported

All confidence intervals will be two-sided 95% confidence intervals.

17. Analysis Populations and Estimand

Except where stated otherwise, all analyses will be conducted under the principle of modified intention-to-treat, whereby all participants are included in their randomised groups, but only those participants who underwent a surgical incision will be included in the analysis.

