Blood transfusion reactions	Binary outcome: any incidence of transfusion reaction	Binary variable 0 = no transfusion reaction; 1 = transfusion reaction	Any blood transfusion reaction following any blood product transfusion

24. Analysis methods

Analysis of primary outcome, and binary secondary/safety outcomes:

For the primary analysis of binary outcomes, we will use log-binomial models adjusting for the stratification variable of diabetes, with random effects for the stratifying variable of site. If that model fails to converge, a log-binomial model with the same link function and adjusting for the stratification variable of diabetes but with cluster-robust standard errors instead of random effects for site. Results will be expressed as risk ratios with 95% confidence intervals.

For analyses based on multiply imputed datasets: if a model fails to converge for more than one quarter of imputed datasets, the model with cluster-robust standard errors will instead be fit.

Days at home up to 30 days after surgery

DAH30 will be compared between groups using median regression adjusting for the stratification variable of diabetes, with cluster robust standard errors for site. DAH-30 is calculated using mortality and hospitalisation data from the date of the index surgery (= Day 0). For example, if a patient died on day 2 after their surgery whilst still an inpatient, they would be assigned zero (0) days at home; if a patient was discharged from hospital on Day 6 after surgery but was subsequently re-admitted for 4 days before their second hospital discharge, then they would be assigned a DAH-30 value of 20. If a patient has complications and spends 16 days in hospital, and then is transferred to a nursing facility for rehabilitation, and spend 24 days there before finally being discharged to their own home, they would be assigned a DAH-30 value of zero (0), even though 30-16-

24 = -10 because the minimum value of DAH-30 should be zero. If a patient dies within 30 days of surgery, irrespective of whether they have spent some time at home, DAH-30 will be scored as zero (0).

In addition to presenting a difference in medians between groups with respect to DAH-30, a difference in lower quartiles (i.e. 25th percentiles) will be presented.

Peak C Reactive protein and volume of red blood cell transfusion

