These outcomes will be compared between groups using mixed effects linear regression models adjusting for the stratification variable of diabetes, with random effects for the stratifying variable of site.

25. Statistical Methods – adjustment for covariates

Supplementary analyses for the primary outcome and the secondary outcome of any red cell transfusion will adjust for any prognostic variables imbalanced at baseline.

For the primary outcome, variables with apparent imbalance out of the following list will be adjusted for:

- Patient age
- ASA physical status
- Diabetes
- Current smoker
- Oral steroid
- Open surgery

For the outcome of any red cell transfusion, variables with apparent imbalance out of the following list will be adjusted for:

- Patient age
- ASA physical status
- Body mass index (weight/height²)
- Chronic renal disease
- Aspirin
- Preoperative haemoglobin
- Open surgery

26. Statistical Methods – subgroup analyses

Subgroup analyses of the primary outcome and any red cell transfusion will be conducted for the following subgroups:

- i) Age strata (\leq 60 yr; 61–70 yr;71–75 yr;>75 yr);
- ii) Patient sex;
- iii) BMI strata (≤ 18.5 ; $\geq 18.5-25.0$; $\geq 25.0-30.0$; $\geq 30.0-35.0$; ≥ 35.0);
- iv) ASA physical status
- v) Diabetes status (i.e. the stratification variable);
- vi) Country;
- vii) Type of GI surgery;
- viii) Duration of surgery (approximate quartiles)

Models for these analyses will be as described in Section 27 for the primary analysis, including terms for the subgroup indicator and interactions between the subgroup and randomised group. Treatment effects in each subgroup will be reported.

27. Missing data reporting and assumptions/statistical methods to handle missing data

Multiple imputation of outcomes will be undertaken if the proportion of missingness of the primary outcome

is >5%.

Missing baseline characteristics will be imputed using single mean imputation. Baseline characteristics of participants who did and did not provide the primary outcome will be compared, and will be used to inform multiple imputation models. T-tests or Wilcoxon rank-sum tests will be used to compare continuous characteristics (depending on whether these had approximately symmetric distributions or not); chi-squared tests will compare categorical characteristics between participants with and without the primary outcome.

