Missing outcome values will be imputed separately by treatment group. Imputation models will include treatment group, diabetes status, and baseline characteristics that appear to be different between participants who provided complete follow up data and participants who did not. Imputation models for continuous outcomes will also include terms for site. Imputation models for binary outcomes will not include terms for site due to the possibility of perfect prediction in small sites.

Initially, imputation via chained equations will be attempted for outcomes, with separate imputation for each outcome if this imputation fails. Binary outcomes will be imputed using logistic regression models, and continuous outcomes imputed via with predictive mean matching from the 5 nearest neighbours. Imputed datasets will be compared to complete data using density plots for continuous outcomes and plots of proportions for binary outcomes.

28. Additional Analyses

As-treated and per protocol analyses of the primary outcome and any red cell transfusion will also be conducted. As noted in the E9(R1) addendum, these additional analyses may be subject to severe bias and may not correspond to a relevant estimand.

Data collected prior to the trial re-start (the "contamination dataset") will also be considered. A table summarizing the baseline characteristics of patients by randomised treatment group will be presented. The primary outcome, red cell transfusion outcomes, and healthcare associated infections will be analysed as described above in this dataset.

29. Harms

Safety outcomes and adverse events will be reported by treatment group.

30. Statistical Software and code

Stata v19 or later will be used (StataCorp. Stata Statistical Software: Release 19. College Station, TX: StataCorp LLC); or R v 4.4.1 or later. Any user-written R packages used will be referenced.

The following code will be applied for the analysis of primary and secondary outcomes:

Primary outcome and binary secondary outcomes:

```
xi: gllamm outcome i.TreatmentGroup i.diabetes, i(site) fam(binomial)
link(log)
```

Primary outcome and binary secondary outcome backup code:

```
binreg outcome i.TreatmentGroup i.diabetes, rr cluster(site)
```

DAH30:

```
qreg2 outcome i.TreatmentGroup i.diabetes, cluster(site)
qreg2 outcome i.TreatmentGroup i.diabetes, cluster(site)
```

Continuous outcomes:

mixed outcome i.TreatmentGroup i.diabetes || site: , reml

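### The main SSI model leaves out baseline variables that the SAP itself calls prognostic; fixing the list in advance is a cheap, small gain in precision, not the repair of an error

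*SAP*

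**What the plan says.** Three places agree on the main model. Section 24 states for binary outcomes: "we will use log-binomial models adjusting for the stratification variable of diabetes, with random effects for the stratifying variable of site". The estimand table in Section 17 gives the same model. The code in Section 30, "xi: gllamm outcome i.TreatmentGroup i.diabetes, i(site) fam(binomial" with a log link, contains treatment, diabetes and site and nothing else. The backup code keeps the same fixed terms and replaces the site random effect with site-clustered standard errors.

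Section 25 introduces a supplementary analysis for SSI and for any red cell transfusion, adjusting for prognostic variables that are imbalanced at baseline. For SSI it says: "For the primary outcome, variables with apparent imbalance out of the following list will be adjusted for". The list has six entries: age, ASA status, diabetes, current smoker, oral steroid and open surgery. Diabetes is already in the main model, so five of the six are outside it. The transfusion list is age, ASA status, body mass index, chronic renal disease, aspirin, preoperative haemoglobin and open surgery. Section 25 gives no threshold for imbalance. Section 22 rules out significance tests between arms and relies on a judgement of clinical importance.

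Section 11 sizes the trial with no allowance for covariates. Its statement is "we require 1,484 per group in order to have 90% power to detect a 30% reduction in SSI to 8.4" (per cent), starting from a control risk of 12% and a two-sided alpha of 0.05.

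**The concern.** In a randomised trial, adjusting for baseline variables that predict the outcome narrows the confidence interval of the treatment effect. The gain comes from how strongly the variables predict the outcome and does not depend on whether the arms look different. The SAP identifies such variables and then ties their use to visible imbalance. That rule does not recover the precision reliably, and it leaves the adjusted model to be chosen after the data are seen.

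At stake are a slightly wider interval for the headline relative risk than the planned data allow, and an adjusted result whose covariates depend on a judgement with no stated criterion.

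**Working it through.** **1. The plan's own figures.** Inputs from Sections 11 and 14: "All applicable statistical tests will be 2-sided and will be performed using a 5% significance level"; control risk p1 = 0.12, treated risk p2 = 0.084, difference d = 0.036, 90% power. With pooled variance and no continuity correction,

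n = [1.96·√(2·p̄·q̄) + 1.2816·√(p1·q1 + p2·q2)]² / d²

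- p̄ = 0.102, so 2·p̄·q̄ = 0.18319, with square root 0.42801.
- p1·q1 + p2·q2 = 0.10560 + 0.07694 = 0.18254, with square root 0.42725.
- n = (0.8389 + 0.5475)² / 0.001296 = 1,484 per group, as stated.

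Section 11 also says: "Were the control group incidence 14%, this sample size provides 94% power to detect a 30% reduction to 9.8"%. The same method at 1,484 per group gives 94.3%. It further says "We plan to enrol 3,300 patients"; with 1,650 per arm, all analysed, power at 12% versus 8.4% is 92.8%. The sizing therefore stands without any covariate gain.

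**2. Gain from adding the five omitted SSI variables.** The SAP gives no covariate effects, so these are assumptions: relative risks of 1.1 per SD of age, 1.3 for higher ASA status, 1.3 for smoking, 1.5 for oral steroid and 1.6 for open surgery. These were then scaled on the log scale by 0.5, 1, 1.5 and 2. For each scenario 600 trials of 1,484 per arm were simulated, and the standardised relative risk was estimated with diabetes alone and with diabetes plus the five variables. A variance ratio r is equivalent to a sample of 1,484 / r per arm, and power then follows from step 1.

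| Effect strength | Variance ratio r | Patients per arm saved, 1,484·(1 − r) | Equivalent n per arm | Power (from 90.0%) |
|---|---|---|---|---|
| 0.5 | 0.9955 | 7 | 1,491 | 90.1% |
| 1 | 0.987 | 19 | 1,504 | 90.4% |
| 1.5 | 0.971 | 43 | 1,528 | 90.8% |
| 2 | 0.947 | 79 | 1,567 | 91.5% |

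**3. Cross-checks.**

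- A separate calculation assumed that the list predicts SSI with a c-statistic of 0.61, 0.66 or 0.69. Variance with diabetes only, divided by variance with the full list, was 1.012, 1.026 and 1.046. These are reductions (1 − 1/ratio) of 1.2%, 2.5% and 4.4%.
- With site effects in both models the ratio was about 1.003 to 1.06, so adjusting for site does not absorb the gain.
- As an outer case, covariates explaining 10% of outcome variance would raise power at 1,484 per arm from 90.0% to 92.8%.

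**4. If surgical approach has to be left out.** In the assumed scenario, each variable's contribution to the variance of log risk is its own variance times its squared log relative risk, using assumed prevalences of 60% (higher ASA), 15% (smoking), 5% (steroid) and 50% (open):

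- age: 1 × 0.0091 = 0.0091
- ASA: 0.24 × 0.0688 = 0.0165
- smoking: 0.1275 × 0.0688 = 0.0088
- steroid: 0.0475 × 0.1644 = 0.0078
- open: 0.25 × 0.2209 = 0.0552

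Open surgery carries 0.0552 / 0.0974, or 57%. Without it the gain is roughly half of that in step 2.

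**5. Cost in convergence.** With a basic fitter, the covariate-adjusted log-binomial model converged in 96%, 89% and 87% of 1,000 simulated trials across the three c-statistics, a failure rate of 4% to 13%.

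**The case against.** The strongest reply is that nothing here is wrong. The sections agree, the model adjusts for both stratification factors, and the sample size was justified without covariates. Section 31 lists the changes from the protocol and the covariate set is not among them, which suggests that it was carried over. The gain is small and every covariate effect behind it is assumed. All of this stands, and it limits the point to an improvement.

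The reply is also right that the gain has a price. A larger log-binomial model fails more often, and the fallback in Sections 24 and 30 is log-binomial too, so it can fail for the same reason. The change needs a further fallback named in advance.

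Two technical limits also stand. The relative risk is collapsible, but that alone does not make a covariate-adjusted log-binomial coefficient equal to the marginal relative risk; this also requires a relative risk that is constant across the covariates. And Section 25 lists open surgery without saying whether it means the planned or the performed approach. Randomisation takes place before surgery, so the approach as performed could be a post-randomisation variable.

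The remaining argument is that Section 25 already deals with chance imbalance. It does so only in a supplementary model picked after inspection, and it does not deliver the precision that comes from a fixed list. That part does not answer the point.

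**Conclusion.** The point holds as a cheap improvement. Always including the named baseline variables would cut the variance of the log relative risk for SSI by about 0.5% to 5% with all five, and by roughly half as much without surgical approach. That is worth 0 to 1.5 power points. The range rests on assumed covariate effects and prevalences.

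A reader might infer that the primary estimate is biased or that the trial falls short of its stated power. The SAP supports neither: randomisation protects the estimate, and 1,484 per group and 94% both reproduce with no adjustment. A reader might also infer that the gain is free, which the convergence figures contradict. For red cell transfusion the same reasoning applies, but the SAP gives nothing from which to size the gain, so none is claimed.

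**What to change.** Before unblinding, amend Sections 17, 24, 25 and 30 and record the change in Section 31:

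- **Main SSI model:** treatment, diabetes, site, age, ASA status, current smoker and oral steroid, always included whatever the observed balance. Add surgical approach only if the approach planned before incision is recorded.
- **Any red cell transfusion:** treatment, diabetes and site, plus age, ASA status, body mass index, chronic renal disease, aspirin and preoperative haemoglobin, with the same condition on surgical approach.
- **Sensitivity analysis:** the present diabetes-plus-site model for both outcomes. Remove the selection by observed imbalance.
- **Fallback:** name one method that is not log-binomial. It can be a modified Poisson model with site-clustered robust errors, or a standardised relative risk from a logistic model, which targets the marginal relative risk directly. Apply it also under the Section 24 rule for non-convergence across imputed datasets.

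The cost is SAP wording, longer model lines and one more prepared estimator. No new data are needed if surgical approach is left out. Section 27 already has a rule for missing baseline values, so patients need not be dropped for missing covariates.

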Other infection	Binary outcome: any incidence of urinary tract (UTI) or "other" infection	Binary variable 0 = no other infection; 1 = UTI or other infection	Any clinical documentation of UTI or other infection
Anastomotic leak	Binary outcome: any incidence of anastomotic leak of any grade	Binary variable 0 = no anastomotic leak; 1 = any anastomotic leak	A defect of the intestinal wall at the anastomotic site (including suture and staple lines of neorectal reservoirs) leading to a communication between the intra- an extra luminal compartments. 1. Grade A - anastomotic

SAP version: Version: 1.0 Date: 13/11/2025

Trial: Tranexamic acid to Reduce Infection after Gastrointestinal Surgery: the TRIGS Trial

			leakage results in no change in patients' management 2. Grade B - leakage requires active therapeutic intervention but is manageable without relaparotomy 3. Grade C - anastomotic
			leakage requires re- laparotomy
Peak-C reactive protein (CRP)	Continuous outcome: concentration of CRP	Continuous outcome with lower limit of 0.	Concentration of CRP on postoperative day 3
Days alive and at home up to 30 days after surgery	Number of days at home up to 30 days after surgery	Continuous outcome with range of 0 to 30	Number of days that a patient is alive and at home up to 30 days after surgery.
Postoperative diagnosis of COVID-19	Binary outcome: any diagnosis of COVID-19 in the 30 days after surgery	Binary variable 0 = no diagnosis of COVID-19; 1 = any diagnosis of COVID-19	Any diagnosis of COVID-19 in the 30-day study period
Safety Outcomes			
Thromboembolism	Binary outcome: any incidence of DVT or PE	Binary variable 0 = no no thromboembolism; 1 = thromboembolism	A clinical diagnosis of DVT or PE up to 30 days after surgery
Seizures	Binary outcome: any incidence of seizure	Binary variable 0 = no seizure; 1 = seizure	A seizure up to 30 days after surgery
Cardiovascular events (MI, stroke)	Binary outcome: any incidence of clinical MI or stroke	Binary variable 0 = no cardiovascular event; 1 = cardiovascular event	A clinical diagnosis of myocardial infarction or stroke up to 30 days after surgery
Anaphylactoid reactions	Binary outcome: any incidence of anaphylactoid reaction post-IV study drug delivery	Binary variable 0 = no anaphylactoid reaction; 1 = anaphylactoid reaction	An anaphylactoid reaction following study drug administration

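### SAP Section 24 applies a log-binomial model with a same-link fallback to very rare safety outcomes; if one arm has no events neither model has a finite risk ratio, and the fallback can report false precision

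*SAP*

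**What the plan says.** The relevant part of SAP Section 24 is headed "Analysis of primary outcome, and binary secondary/safety outcomes", so one rule covers all three groups of outcomes. For these, "we will use log-binomial models adjusting for the stratification variable of diabetes, with random effects for the stratifying variable of site". The backup is triggered by non-convergence only: "If that model fails to converge, a log-binomial model with the same link function and adjusting for the stratification variable of diabetes". It differs from the first model in one respect, its handling of site: "but with cluster-robust standard errors instead of random effects for site". The reporting rule is "Results will be expressed as risk ratios with 95% confidence intervals". Section 14 adds: "All applicable statistical tests will be 2-sided and will be performed using a 5% significance level".

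Section 23 lists five binary safety outcomes: thromboembolism, seizures ("any incidence of seizure"), MI or stroke, anaphylactoid reactions and transfusion reactions. No expected rate is given for any of them.

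Section 30 gives the backup command ("binreg outcome i.TreatmentGroup i.diabetes, rr cluster(site"), but labels it for the primary and binary secondary outcomes. Section 29 says only that harms are reported by treatment group. Section 27 recognises perfect prediction, but only for the imputation models. No section sets a minimum event count, an exact or penalised method, or a descriptive-only rule for the outcome models.

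**The concern.** A log-binomial model estimates the log of the ratio of two risks. If one observed risk is zero, the likelihood keeps improving as the coefficient moves towards plus or minus infinity, so no finite maximum exists. Replacing random site effects with a different variance estimator leaves the likelihood's link and treatment term as they were, so the prespecified fallback cannot cure the failure that may have triggered it.

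The robust variance adds a further hazard. It depends on how the few observed events are spread over sites, and it can stay small while the coefficient runs off. Software that stops at a large finite coefficient can then print a narrow interval far from 1.

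At stake is the reporting of named safety outcomes. One to three events, all in one arm, could appear as a harm or as protection with an extreme p-value. Alternatively the model gives nothing usable, and the replacement method is chosen after the data have been seen.

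**Working it through.** **Inputs.** From the SAP: planned enrolment 3,300 and 30% diabetic (Section 11); the two-sided 5% level (Section 14); the model, covariate and clustering (Section 24). Assumed: 1,650 per arm (equal allocation, inferred from the per-group sample size), 50 sites, and safety risks of 0.05% to 0.5%.

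**The plan's own figure.** The SAP states none for safety outcomes. Its sample size for SSI (12% vs 8.4%, 90% power) reproduces:

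n = [1.960·√(2·0.102·0.898) + 1.282·√(0.12·0.88 + 0.084·0.916)]² / 0.036² ≈ 1,484 per group.

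**How often one arm is empty.** With risk r in both arms, q = (1 − r)^1650 is the chance that a given arm has no events. The chance that exactly one arm is empty is 2q(1 − q).

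| Assumed risk | q | Exactly one arm empty |
|---|---|---|
| 0.05% | 0.438 | 49% |
| 0.1% | 0.192 | 31% |
| 0.2% | 0.0368 | 7% |
| 0.3% | 0.0070 | 1.4% |
| 0.5% | 0.00026 | 0.05% |

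At 0.05% both arms are empty in a further q² = 19% of trials, where there is nothing to compare.

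**What the fallback does.** The fallback was fitted as a binomial GLM with log link, treatment and diabetes as covariates, and variance clustered on site. The software was statsmodels, not Stata.

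- *Why the standard error stays finite.* When one arm is empty, the robust variance of the log risk ratio is close to the sum over sites of the squared event shares, times G/(G − 1) for G sites. With k events at k different sites this is (1/k)·G/(G − 1). For k = 3 and G = 50: √((1/3)(50/49)) = 0.58.
- *Events in the placebo (reference) arm only.* The fits reported convergence with log risk ratios of about −20 to −22. Robust standard errors were about 1.02, 0.73 and 0.59 for 1, 2 and 3 events vs 0. For 3 vs 0, z ≈ −21.1/0.59 ≈ −36, so p is far below 0.001. Fisher's exact p for the same counts is 1.0, 0.50 and 0.25.
- *Source of the false precision.* The model-based standard error in such fits was about 13,000 to 18,000, with p about 0.999. The small p-value therefore comes from the robust variance.
- *Events in the TxA arm only, placebo as reference.* The output was unstable. The robust standard error was missing in several fits; one 5 vs 0 fit gave 9.8 with p = 0.027, against Fisher's 0.062. With the treatment coding reversed, which is the same model, 3 TxA vs 0 placebo events gave a risk ratio of about 1.8 × 10⁹, 95% CI about 5.6 × 10⁸ to 5.5 × 10⁹.
- *Number of sites.* With that reversed coding, 20 and 90 sites gave the same picture.

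**What an exact method gives.** For k events vs 0 in equal arms, the lower 95% limit for the share of events in the arm with events is L = 0.025^(1/k). The risk ratio limit is L/(1 − L), with no finite upper limit.

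- 2 vs 0: L = 0.158, lower limit 0.19, Fisher's p = 0.50.
- 3 vs 0: L = 0.292, lower limit 0.41, Fisher's p = 0.25.
- 5 vs 0: L = 0.478, lower limit 0.92, Fisher's p = 0.062.

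All three intervals include 1.

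**The case against.** The strongest reply is that a false p-value needs a chain of events. One arm must be empty, the random-effects model must fail to converge, and the fallback must then report convergence on a likelihood with no maximum. Neither the gllamm command nor Stata's binreg was run. If the first-line model stops at a large coefficient with a model-based standard error, the interval is enormous and nothing looks significant. That stands. A reader might take the empty-arm probabilities above as the plan's false-positive rates; the documents do not support this, because the fallback applies only after non-convergence.

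Rarity is also assumed. A reader might infer that all five safety outcomes are at risk. The SAP gives no rates, and at 0.5% or more the problem is negligible, so thromboembolism and MI or stroke may well be unaffected.

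Section 30 does not label its backup command for safety outcomes. That stands too, but Section 24 names safety outcomes expressly, so the rule applies whatever the code label says.

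Finally, counts by arm will be reported under Section 29, and a risk ratio near 10⁹ is visibly a failed fit. This makes unnoticed publication less likely. It does not supply a prespecified analysis, and whoever notices must then choose a method with the data in view.

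**Conclusion.** The point holds in a limited form. Section 24 promises a risk ratio with a 95% confidence interval for every binary safety outcome. When exactly one arm is empty, no finite estimate exists under the model or its only fallback. The fallback can then give a falsely precise result, or an erratic or missing standard error, and the SAP stops there. That it *will* give a false p-value is not shown.

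The size depends on assumed risks with 1,650 per arm: material at about 0.2% or below, small at 0.3%, negligible at 0.5%. Seizures, anaphylactoid reactions and transfusion reactions are the plausible candidates. SSI, planned at 8.4% to 14%, is not affected. The change should be made before unblinding; it does not bear on the trial's main conclusion.

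**What to change.** Add to Section 24: 'For any binary outcome with zero events in at least one arm, or fewer than a prespecified small total number of events (e.g. 10), no regression model is fitted; counts and percentages by arm, Fisher's exact p-value and an exact 95% CI (for the risk ratio, or for the risk difference) are reported.'

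The SAP should fix one threshold and one scale. Ten is a judgement, and another small number would serve if set before unblinding. An exact conditional interval keeps the SAP's risk ratio scale. A risk difference interval has the advantage of being finite when an arm is empty. Section 30 should state which code applies to safety outcomes.

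A Poisson model with robust standard errors is no substitute here: it uses the same log link and has the same zero-cell defect.

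The cost is a sentence of SAP text and a few lines of code. The downside is that these sparse outcomes are not adjusted for diabetes or site, an adjustment that so few events could hardly support.
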